### 5.3 LIFESTYLE CONSIDERATIONS

Not applicable.

### 5.4 SCREEN FAILURES

Individuals who do not meet the criteria for participation in this trial (screen failure) because of an early delivery or delivery at a time other than their scheduled delivery time may be rescreened but cannot participate in the study. Rescreened participants should be assigned the same participant number as for the initial screening.

### 5.5 STRATEGIES FOR RECRUITMENT AND RETENTION

Potential study participants will be approached by study personnel at time of presentation for her scheduled cesarean delivery at Labor and Delivery at the Long Island Jewish Medical Center.

There are approximately 1 – 2 scheduled cesarean deliveries per day between the Ambulatory Care Clinic, Garden City OBGYN (Long Island Jewish Medical Center/Northwell Health OB/GYN practice) and the Women's Comprehensive Care Center (Long Island Jewish Medical Center Faculty practice). Approximately 34% of these patients are obese. We anticipate a 75% accrual rate.

Patients will be identified and approached while they are waiting for cesarean delivery surgery time by study personnel. Study personnel will show the patients an example of a PICO dressing and a standard of care dressing and explain study protocol and procedures.

A pregnant participant population must be used as subjects in this study because the primary endpoint is SSO and SSI incidence in patients who are undergoing cesarean delivery.

Participants will not be compensated for participation in the study.

## 6 STUDY INTERVENTION

### 6.1 STUDY INTERVENTION(S) ADMINISTRATION

#### 6.1.1 STUDY INTERVENTION DESCRIPTION

The PICO Single Use Negative Pressure Wound Therapy Device (Smith and Nephew Healthcare, Hull, United Kingdom) is a non-significant-risk, FDA Class II, medical device commercially available in the USA. The PICO unit is a single patient use, battery-powered, disposable unit that can provide continuous 80 - 125 mmHg negative pressure over a 5 to 7-day therapy period. It is an easy to use device that also provides audible and visual alerts for low battery, maximum canister volume, and leak conditions. Additional alerts include system error and device life-cycle expiration (7 days). It is contained in a water-resistant housing, which allows the subject to lightly shower with the device. Wound fluids are contained within the 45 mL canister.

The dressing is applied to the wound and extra strips are placed over the outside edge to help hold the dressing in place. When the pump is turned on, air is pulled out of the dressing and excess fluid from the wound will start to enter the dressing. The dressing helps to prevent bacteria from entering the wound. It may also improve blood flow to the wound which will help it to heal.

The standard-of-care is consistent with the national standard for dressing Cesarean section incisions and includes, but not limited to, coverage of the sutured incision with sterile gauze and non-penetrable barrier (e.g., Tegaderm™). The non-penetrable barrier may be left in place for a minimum of 1 day and no longer than 2 days ( $\pm$  4 hours) to promote epithelialization of the surgical incision edges. After the dressing is removed, the surgical site is left exposed to air to promote further healing. Other therapies include traditional gauze dressings with or without advanced therapies such as hydrocolloids, growth factors, and Negative Pressure Wound Therapies.

#### 6.1.2 DOSING AND ADMINISTRATION

The PICO dressing provides 80 - 125 mmHg negative pressure over a 5 day therapy period as a standard setting and this will be used in all patients.

Patients will be taught how to remove the dressing at home after the total 5-day period. Dressing removal is not difficult and should not cause excess pain or discomfort. In order to remove the dressing, the pump is disconnected and the dressing is removed by gently pulling the adhesive edges. The entire dressing and pump can be disposed of in the garbage.

### 6.2 PREPARATION/HANDLING/STORAGE/ACCOUNTABILITY

## 6.2.1 ACQUISITION AND ACCOUNTABILITY

The PICO dressing and supplies for the pressure dressing are available on the Long Island Jewish Medical Center Labor and Delivery Unit. Study personnel will obtain dressing and apply dressing.

## 6.2.2 FORMULATION, APPEARANCE, PACKAGING, AND LABELING

The Smith and Nephew PICO device (Figure 1) is packaged for single use and does not need returning or sterilization. The battery pack retains its charge for 7 days delivering a continuous negative pressure. The dressing is designed in 4 layers: top film layer with a high moisture vapor transmission rate (MVTR) allows one-way transpiration of exudate vapor, proprietary absorbent layer moves exudate away from the wound and initiates evaporation, airlock layer maintains open airflow and allows even distribution of negative pressure across the dressing, and the wound contact layer is composed of silicon and does not lead to in-growth of granulation tissue into the dressing material to decrease pain with removal. The pump is a water-resistant, quiet, pocket-sized, canister-free system that uses two AA lithium batteries that last for the 5 – 7 day therapy. The device is packaged in a disposable cardboard box (Figure 2) and can be kept at room temperature. PICO™ is supplied in a pack that can be taken off the shelf when required. It contains a single use pump, which lasts for 7 days and two individually packed dressings and fixation strips (allowing for the wound to be inspected during those 7 days).

### PICO specifics from manufacturer product safety data sheet:

Dressing: Laminate of silicone/acrylic adhesive coated polyurethane films to polyethylene layer and polyacrylate/cellulose airlaid layer. A polyurethane port and an acrylic copolymer/nylon filter membrane are bonded to the laminate using acrylic adhesive. PVC tubing is also bonded to the polyurethane port using an acrylic adhesive. Laminate is placed on HDPE handles.

Secondary fixation strips: Laminate of acrylic adhesive coated on polyurethane film placed between polyethylene, polypropylene and paper carriers.

Pump: Internal components consist of PCBA (Printed Circuit Board Assembly consisting of multiple electronic components, PCB and soldered joints), electric motor driven diaphragm pump, air manifold (thermoplastic elastomer), wiring, connections and steel battery contacts. External components consist of 2 case halves (ABS thermoplastic), air inlet connection (ABS thermoplastic), button (thermoplastic elastomer), lenses (polystyrene) and battery cover (ABS thermoplastic).

A 10 x 30cm PICO dressing size fits most cesarean section incisions, and larger and smaller sized dressings are available.

The standard pressure dressing is composed of Telfa®, a non-adherent wound dressing which consists of absorbent cotton fibers impregnated with polyhexamethylene biguanide enclosed in a sleeve of thermoplastic polymers, cotton 4" x 4" sterile mesh gauze manufactured by Medtronic (Minneapolis, MN, USA) and a non-penetrable barrier (e.g., tape or Tegaderm™ adhesive film (3M, USA).

Figure 1:

Figure 2:

### 6.2.3 PRODUCT STORAGE AND STABILITY

Both the standard dressing supplies and the PICO dressing can be stored in the operating room storage units. Both must be stored in a cool, dry place <25°C and kept away from sources of ignition and strong light sources.

### 6.2.4 PREPARATION

Both dressing are easily applied in a few minutes. There is no required thawing, diluting, mixing, reconstitution/preparation, or difficult assembly.

How to apply instructions from PICO package insert:

#### Application

1. Remove any excess hair to ensure close approximation of the dressing to the wound. If necessary, irrigate the wound with sterile saline and pat the wound dry.
2. Using a clean technique, peel off the central release handle and place the dressing centrally over the wound to reduce the chance of wound fluid coming into contact with the port. The port should be uppermost from the wound (depending on the patient's primary position), placed on intact skin and not extend over the wound to prevent fluid pooling around the port and blocking the negative pressure. Remove the other two

handles and smooth the dressing around the wound to prevent creasing. Reposition if required to ensure border is not creased.

3. Once the dressing is in place, remove the pump and the batteries from the tray. Insert the batteries. Replace the cover. Following this all three lights should flash once.

4. Join the pump to the dressing by twisting together the tubing connectors. Press the orange button to start the application of negative pressure. The green light will start to flash indicating the system is working properly.

Depending on the size of the wound, the pump should take up to 30 seconds to establish negative pressure wound therapy.

5. If using SKIN-PREP™ prior to application of the fixation strips (see Precautions), wipe the area surrounding the dressing and allow skin to dry.

6. Apply the fixation strips to each of the four sides of the dressing. Remove top carrier on the strip after each one has been applied. These strips maintain the seal over the wear time of the dressing. In awkward areas, it may be useful to apply the strips to help achieve a seal prior to switching on the pump. Place each strip so that it overlaps the dressing border by approximately 1cm (2/5in.). Ensure tubing is not twisted or trapped between clothing.

Please note that if at any time the fixation strips are removed, the dressing should also be replaced.

### 6.3 MEASURES TO MINIMIZE BIAS: RANDOMIZATION AND BLINDING

This trial tests a clinical intervention that is not amenable to protection against performance bias through the blinding of participants, clinical staff or data collectors. There will be no blinding in the study. Neither the participants nor the physicians will be blinded to the study treatment they are randomized to.

The Biostatistics Unit at the Feinstein Institute for Medical Research [BU-FIMR] will develop a randomization plan for the study using the Biostatistics Randomization Management System [BRMS]. BRMS is a secure, HIPAA-compliant, web-based application that allows investigators to randomize subjects into randomized clinical trials (RCTs) using a personal computer with internet access. The BRMS allows for multi-center, stratified, and single/double blinded RCTs. Randomization notifications are automatically sent to the PI and other authorized personnel. BRMS maintains compliance in RCTs.

A randomization schema will be generated by the BU-FIMR using the method of permuted blocks. Subjects will be randomly assigned in a 1:1 ratio to either 'PICO' or 'STANDARD DRESSING'. Details of the randomization procedure, including required record keeping will be further developed upon approval of the protocol.

The RA will randomize participants in the operating room at the start of their cesarean procedure and advise the operating obstetrician and nursing staff of the allocated treatment as close to the end of the procedure as possible in order to minimize performance bias.

To minimize the potential for outcome detection bias, an expert statistician, blinded to group allocation, will assess the data to determine the primary outcome.

Subjective outcomes (SSI/SSOs) are reported by patients or observed by study personnel, who cannot be blinded because they need to check the dressings.

Outcome assessors will be masked to allocation.

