### 5.1 INCLUSION CRITERIA

In order to be eligible to participate in this study, an individual must meet all of the following criteria:

1. Provision of signed and dated informed consent form
2. Stated willingness to comply with all study procedures and availability for the duration of the study; willing and able to return for all scheduled and required study visits
3. Female, aged 18 – 55 years
4.  $\text{BMI} \geq 35 \text{ kg/m}^2$  in the 42 days prior to surgery
5. In good general health as evidenced by medical history with a 24 – 41 weeks gestational age pregnancy scheduled for cesarean delivery for any routine indication (repeat procedure, breech presentation, abnormal placentation, uterine anomaly, maternal medical condition, or elective)
6. Ability to and willingness to adhere to the PICO negative pressure wound therapy regimen
7. Surgical skin site preparation with chlorhexidine gluconate solution (ChloraPrep©)
8. Received preoperative surgical prophylaxis antibiotics as per protocol
9. Surgical incision that can be covered completely by the NPWT skin system
10. Pre-operatively assessed to undergo a procedure with a CDC Wound Classification of:
  - a. Class I (Clean): An uninfected operative wound in which no inflammation is encountered and the respiratory, alimentary, genital, or uninfected urinary tract is not entered  
- OR -
  - b. Class II (Clean Contaminated): An operative wound in which the respiratory, alimentary, genital, or uninfected urinary tract are entered under controlled conditions and without unusual contamination
11. Wound hemostasis has been achieved

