### 5.2 EXCLUSION CRITERIA

An individual who meets any of the following criteria will be excluded from participation in this study:

1. Cesarean delivery before fetal viability (24 0/7 weeks gestational age)
2. Unplanned Cesarean delivery

3. Fetal death
4. Known allergic reactions to components of the PICO NPWT system
5. Systemic bacterial or fungal infection at the time of surgery
6. Diagnosis of systemic or remote-site skin infections at time of delivery
7. Treatment with another investigational drug or other intervention within 7 days prior to cesarean delivery or 42 +/- 10 days after cesarean delivery
8. Delivery for suspected intrauterine infection (defined as maternal fever plus one clinical criteria)
9. Critical illness or immune-compromising disease (eg acquired immunodeficiency syndrome)
10. Chronic steroid use
11. Pre-operatively assessed to have a CDC Wound Classification of:
  - Class III (Contaminated): Open, fresh, accidental wounds, and/or major breaks in sterile technique or gross spillage from the gastrointestinal tract
    - OR -
  - Class IV (Dirty-Infected): Old traumatic wounds with retained devitalized tissue and those that involve existing clinical infection or perforated viscera
12. High-risk for anesthesia (American Society of Anesthesiologists [ASA] class P4 – P6)
13. Intra-operative hemorrhage requiring blood transfusion, disseminated-intravascular coagulopathy (DIC) or any other medical or surgical condition during the Cesarean section deemed by the investigator to pose a prohibitively high risk for surgical re-exploration
14. Life expectancy of < 12 months
15. Unable to speak or understand English, with no interpreter available

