## 8 STUDY ASSESSMENTS AND PROCEDURES

## 8.1 EFFICACY ASSESSMENTS

Screening procedures and evaluations may be performed on the day of enrollment but no more than 10 days prior to the day of enrollment. The screening process will be a discussion with the patient and review of medical history and height and weight to determine eligibility, and explanation of the study rational and study protocol, and demonstration of the two dressing options. Informed consent will then be obtained and patients will have the opportunity to ask questions.

The study intervention will be administered at the end of the scheduled cesarean delivery procedure. Standard dressings will be removed on postoperative day 1 as per current protocol and PICO NPWT dressings will be changed if necessary in the hospital and removed on postoperative day 5 by the patient at home.

**Procedures that will be completed during the study as part of regular standard of clinical care:** the post-operative visits on day 7 – 14 and 42 +/- 10 days are part of regular standard of clinical care and the outcomes and incision assessments after the participating patients leave the hospital will be performed by skilled residents and attending physicians at these visits. Charts will be reviewed to ascertain if SSO/SSIs were diagnosed or SII were necessary.

During these regularly scheduled visits, a **physical examination and incision assessment** will be performed including weight, abdominal exam, incision exam, and all regular postoperative visit exams including breast and pelvic (at the 42 +/- 10 day visit only) as part of the routine standard of care.

If follow-up visits or unscheduled visits are required for treatment of SSO/SSIs or SII, information regarding the type of SSO or SII required will be obtained from review of the medical chart.

**Surgical Site Occurrences include:** unanticipated local inflammatory response, prolonged drainage, fluid collection, dehiscence, surgical site infection (SSI). SSI is diagnosed using the following criteria: warmth to touch, pain with palpation, skin redness, irritation, or induration, large amount of drainage or purulent drainage, fluctuance suspicious for wound abscess, fever, and/or wound odor.

**Surgical Site Interventions include:** Antimicrobials for surgical site infection, surgical drainage of the incision, surgical incision packing, adjunctive negative pressure therapy, debridement, or re-operation.

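### Section 6.3 draws the allocation at the start of the cesarean, before the intra-operative eligibility criteria can be settled; the expected bias is small and the correction is cheap

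*Protocol*

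**What the plan says.** **Timing.** Protocol 6.3 fixes the draw: "The RA will randomize participants in the operating room at the start of their cesarean procedure". The research assistant (RA) then tells the obstetrician and nurses the arm as near to the end of the operation as possible. Section 8.2 sets only an earliest time for randomisation (arrival on labor and delivery) and repeats the late disclosure. Section 8.1 places the dressing itself later: "The study intervention will be administered at the end of the scheduled cesarean delivery procedure".

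**Eligibility.** Section 5.1 says that "an individual must meet all of the following criteria", and criterion 11 on that list is "Wound hemostasis has been achieved". Exclusion 13 in 5.2 covers "Intra-operative hemorrhage requiring blood transfusion", coagulopathy, and any other condition during the operation that is "deemed by the investigator to pose a prohibitively high risk for surgical re-exploration". Inclusion 9 requires that the dressing can cover the incision completely. The synopsis and the opening of section 5 require subcuticular skin closure.

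**What happens to women who fail.** Section 5.4 treats as screen failures only those who deliver early or off schedule. Section 7.2 allows withdrawal when an exclusion criterion is newly met or newly recognised, and allows replacement. Section 9.3 bases the primary analysis on women who had surgery and received the intervention.

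**What is left open.** Section 6.3 says: "Details of the randomization procedure, including required record keeping will be further developed upon approval of the protocol". It also says: "Randomization notifications are automatically sent to the PI and other authorized personnel".

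**The concern.** Read literally, no woman can satisfy 5.1 when 6.3 has her randomised. Eligibility is completed after an allocation exists, and part of exclusion 13 is a matter of investigator judgement. The trial is open-label. If anyone with a say in that judgement knows the arm, the decision to exclude can depend on it, and the groups that remain are no longer purely the product of randomisation.

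The protocol also provides the route by which such women disappear from the comparison: withdrawal and replacement under 7.2, and a primary set in 9.3 limited to those who received the intervention. A woman likely to bleed, collect fluid or need re-exploration is plausibly at above-average risk of a surgical site occurrence (SSO). Removing more of these women from one arm would make that arm look better.

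**Working it through.** **1. The plan's own figure.** Section 9.2 gives 18% vs 8%, alpha 0.05, power 80%, 180 evaluable per group and 200 recruited per group. For a two-sided test without continuity correction:

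n = [1.96·√(2·0.13·0.87) + 0.8416·√(0.18·0.82 + 0.08·0.92)]² / 0.10² = (0.932 + 0.396)² / 0.01 ≈ 176.4, so 177 per group.

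The planned 180 gives 80.8% power, and 180/0.90 = 200. The sample size reproduces and is not in dispute.

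**2. Order of events.**

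| Step | When | Section |
|---|---|---|
| Allocation drawn | Start of operation | 6.3 |
| Exclusion 13 settled | During operation | 5.2 |
| Hemostasis (inclusion 11) | During or at end of operation | 5.1 |
| Coverage (inclusion 9), subcuticular closure | Possibly only near the end | 5.1, synopsis, 5 |
| Arm told to operating team | As near the end as possible | 6.3, 8.2 |
| Dressing applied | End of operation | 8.1 |

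All 2 × 200 = 400 planned women are allocated before inclusion 11 can be met (the synopsis also gives 396). This counts the ordering, not harm: a woman who later passes every criterion is unaffected.

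**3. How many could fail.** The protocol gives no rate. Assuming e = 1%, 2% or 5%, the number of randomised women who fail is 400·e = 4, 8 or 20.

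**4. Size of the bias.** Assume no true effect (18% in both arms). Let d be the share of exclusion decisions exposed to the allocation, and let every exposed decision become an extra exclusion in the PICO arm only, so that the excess is x = e·d. Let r be the SSO risk of the women removed. Then

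PICO rate = (0.18 − r·x) / (1 − x).

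Rejection is for the two-sided 5% pooled chi-square test with 180 per arm. With r = 40% (assumed):

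| e | d | x | PICO rate | Shift (points) | Rejection |
|---|---|---|---|---|---|
| 1% | 0.25 | 0.25% | 17.945% | 0.06 | 5.00% |
| 2% | 0.25 | 0.50% | 17.889% | 0.11 | 5.01% |
| 5% | 0.25 | 1.25% | 17.722% | 0.28 | 5.05% |
| 1% | 1 | 1% | 17.778% | 0.22 | 5.03% |
| 2% | 1 | 2% | 17.551% | 0.45 | 5.14% |
| 5% | 1 | 5% | 16.842% | 1.16 | 5.96% |

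The rows with d = 0.25 credit late disclosure. They correspond to 0.5, 1 and 2.5 extra exclusions among 200 PICO women. The rows with d = 1 give no credit.

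Last row in full: (0.18 − 0.40·0.05)/0.95 = 0.16842, so the shift is 0.01158. Mean rate 0.17421; SE = √(2·0.17421·0.82579/180) = 0.0400; shift/SE = 0.29. Rejection ≈ Φ(−1.67) + Φ(−2.25) ≈ 0.0474 + 0.0122 ≈ 0.060.

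**5. Sensitivity.** At x = 5%, r = 30% gives 17.368% (0.63 points) and r = 50% gives 16.316% (1.68 points). At r = 54%, three times the average, the shift is 1.89 points with 7.6% rejection (180 control vs 171 PICO). If exclusions are blind to arm, the expected difference is 0 in every case.

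**The case against.** The strongest reply is that the protocol already blocks the mechanism. Bias needs the person who excludes to know the arm, and 6.3 and 8.2 both withhold it from the operating team until near the end. Transfusion and coagulopathy are largely matters of fact; only the last clause of exclusion 13 is discretionary. With that safeguard credited, the shift is at most 0.28 points, on rates that are all assumed. This stands, and it is why the point is minor. What it does not answer is that disclosure is not tied to a recorded eligibility decision, that the RA already holds the arm during the operation, and that inclusion 11 cannot be met at the stated time.

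Four stronger readings are tempting, and the protocol does not support them:

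- *The analysis could not repair the damage.* Following and analysing all randomised women as assigned would largely repair it. Section 9.3 itself has wording that keeps women who withdraw in their assigned group, beside wording that restricts the set.
- *The automatic notification unblinds the principal investigator.* The sentence is part of a general description of the randomisation system and does not say that the arm is shown.
- *The trial loses power.* Section 7.2 allows replacement. Even without it, a 5% loss leaves 200·0.95·0.90 = 171 evaluable per group and 78.8% power.
- *The matter is merely deferred.* Section 6.3 does leave procedural detail for later, but the time of the draw is already fixed.

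**Conclusion.** The ordering defect is in the text and is certain: sections 5.1 and 5.2 cannot be completed at the time that 6.3 sets for randomisation, and 7.2 and 9.3 allow women who then fail to leave the primary comparison. Its expected effect is small: no bias if exclusions are blind to arm, and about 0.06 to 0.3 points with type I error at most 5.05% when late disclosure is credited. The assumed worst case of a 5% PICO-only excess gives about 1.2 points and 6%, against a planned difference of 10 points.

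These sizes rest wholly on assumptions about the failure rate, the share of exposed decisions, the SSO risk of the excluded women and exclusion in one direction only. The protocol gives none of them. A reader might infer that the primary result would be materially biased; these figures do not support that unless differential exclusion were far more common than late disclosure makes likely. It is a cheap improvement of minor severity.

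**What to change.** **Preferred.** In 6.3, and consistently in 8.2, state that the RA draws the allocation from the web system when skin closure is complete and before the dressing is applied, after all intra-operative eligibility criteria (inclusions 9 and 11, exclusion 13, subcuticular closure) have been confirmed and logged with the time. In 5.4, add that women who fail before that point are screen failures and are not randomised.

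**If the early draw is kept.** Log the eligibility decision before the arm is disclosed to anyone involved in it, follow and analyse all randomised women as assigned, and reconcile 7.2 and 9.3 with that. In either case, say in 6.3 whether the automatic notification shows the arm.

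**Limits.** A condition recognised after closure can still lead to withdrawal under 7.2, so the later draw reduces post-randomisation exclusions but does not end them. The replacement rule and the analysis set still have to be made consistent.

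**Cost.** Protocol wording and a change in the RA's workflow. The RA and the web system are the same, both dressings are already on the unit (6.2.1), and they go on in a few minutes (6.2.4). The downside is slight time pressure at the end of surgery, with a small added risk of a wrong dressing. That matters because 9.3 currently excludes women who receive the wrong dressing by accident, which is itself an exclusion after randomisation.
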